#### **8.4.2 Method of Detecting AEs, SAEs, and Other Reportable Safety Events**

Care will be taken not to introduce bias when detecting AEs and/or SAEs and other reportable safety events. Open-ended and nonleading verbal questioning of the participant is the preferred method to inquire about AE occurrence.

#### **8.4.3 Follow-up of AE, SAE, and Other Reportable Safety Event Information**

After the initial AE/SAE report, the investigator is required to proactively follow each participant at subsequent visits/contacts. All AEs, SAEs, and other reportable safety events, including pregnancy and exposure during breastfeeding, ECIs, cancer, and overdose will be followed until resolution, stabilization, until the event is otherwise explained, or the participant is lost to follow-up (as defined in Section 7.3). In addition, the investigator will make every attempt to follow all nonserious AEs that occur in randomized participants for outcome. Further information on follow-up procedures is given in Appendix 3.

#### **8.4.4 Regulatory Reporting Requirements for SAE**

Prompt notification (within 24 hours) by the investigator to the Sponsor of SAE is essential so that legal obligations and ethical responsibilities towards the safety of participants and the safety of a study intervention under clinical investigation are met.

The Sponsor has a legal responsibility to notify both the local regulatory authority and other regulatory agencies about the safety of a study intervention under clinical investigation. The Sponsor will comply with country-specific regulatory requirements and global laws and regulations relating to safety reporting to regulatory authorities, IRB/IECs, and investigators.

Investigator safety reports must be prepared for SUSARs according to local regulatory requirements and Sponsor policy and forwarded to investigators as necessary.

An investigator who receives an investigator safety report describing an SAE or other specific safety information (eg, summary or listing of SAE) from the Sponsor will file it along with the IB and will notify the IRB/IEC, if appropriate according to local requirements.

#### **8.4.5 Pregnancy and Exposure During Breastfeeding**

Although pregnancy and infant exposure during breastfeeding are not considered AEs, any pregnancy or infant exposure during breastfeeding in a participant (spontaneously reported to the investigator or their designee) that occurs during the study are reportable to the Sponsor.

All reported pregnancies must be followed to the completion/termination of the pregnancy. Pregnancy outcomes of spontaneous abortion, missed abortion, benign hydatidiform mole, blighted ovum, fetal death, intrauterine death, miscarriage, and stillbirth must be reported as serious events (Important Medical Events). If the pregnancy continues to term, the outcome (health of infant) must also be reported.

#### **8.4.6 Disease-related Events and/or Disease-related Outcomes Not Qualifying as AEs or SAEs**

This section is not applicable to this study.

#### **8.4.7 Events of Clinical Interest**

Selected serious and nonserious AEs are also known as ECIs and must be reported to the Sponsor.

Events of clinical interest for this study include:

1. An overdose of Sponsor's product, as defined in Section 8.5.
2. An elevated AST or ALT lab value that is greater than or equal to 3X the upper limit of normal and an elevated total bilirubin lab value that is greater than or equal to 2X the upper limit of normal and, at the same time, an alkaline phosphatase lab value that is less than 2X the upper limit of normal, as determined by way of protocol-specified laboratory testing or unscheduled laboratory testing.\*

\*Note: These criteria are based upon available regulatory guidance documents. The purpose of the criteria is to specify a threshold of abnormal hepatic tests that must trigger an additional evaluation for an underlying etiology. The study site guidance for assessment and follow up of these criteria can be found in the Investigator Study File Binder (or equivalent).

It may also be appropriate to conduct additional evaluation for an underlying etiology in the setting of abnormalities of liver blood tests including AST, ALT, bilirubin, and alkaline phosphatase that do not meet the criteria noted above. In these cases, the decision to proceed with additional evaluation will be made through consultation between the study investigators and the Sponsor Clinical Director. However, abnormalities of liver blood tests that do not meet the criteria noted above are not ECIs for this study.

3. Dystonia
4. New or worsening tardive dyskinesia
5. QTcF interval of  $\geq 500$  msec (the average of 3 QTcFs will be used)
6. Suicidal ideation, suicidal behavior

#### **8.5 Treatment of Overdose**

For purposes of this study, an overdose will be defined as any dose of any drug administered as part of the study exceeding the dose prescribed by the protocol. It is up to the investigator or the reporting physician to decide whether a dose is to be considered an overdose, in consultation with the Sponsor.

## 8.6 Pharmacokinetics

The decision as to which plasma samples collected will be assayed for evaluation of PK/PD will be collaboratively determined by the Sponsor (eg, samples at lower doses may not be assayed if samples at higher doses reveal undetectable drug concentrations). If indicated, these samples may also be assayed and/or pooled for assay in an exploratory manner for metabolites and/or additional PD markers.

### 8.6.1 Blood Collection for Plasma MK-8189

Sample collection, storage, and shipment instructions for plasma samples will be provided in the operations manual.

## 8.7 Pharmacodynamics

Pharmacodynamic parameters will not be evaluated in this study.

## 8.8 Biomarkers

Collection of samples for other biomarker research is also part of this study. The following samples for biomarker research are required and will be collected from all participants as specified in the SoA:

- Blood for Genetic Analysis

### 8.8.1 Planned Genetic Analysis Sample Collection

The planned genetic analysis sample will be drawn for CYP2C9 genotyping and for planned analysis of the association between genetic variants in DNA and drug response. If the IRB/IEC does not approve of the planned analysis of the association between DNA variation and drug response, or if there is a local law or regulation prohibiting the same, data analysis will be limited to CYP2C9. Leftover extracted DNA will be stored for future biomedical research if the participant signs the future biomedical research consent.

Sample collection, storage, and shipment instructions for planned genetic analysis samples will be provided in the operations/laboratory manual.

## 8.9 Future Biomedical Research Sample Collection

If the participant signs the future biomedical research consent, the following specimens will be obtained as part of future biomedical research:

- Leftover DNA for future research
- Leftover main study plasma from MK-8189 and/or metabolites assay stored for future research.

## 8.10 Visit Requirements

Visit requirements are outlined in Section 1.3. Specific procedure-related details are provided in Section 8.

### 8.10.1 Screening

Approximately 4 weeks prior to intervention allocation/randomization, potential participants will be evaluated to determine that they fulfill the entry requirements as set forth in Section 5.

Participants may be rescreened after consultation with the Sponsor. Rescreening should include all screening procedures listed in the SoA, including consent review. Rescreen procedures cannot be conducted the day prior to intervention allocation/randomization if there are Day -1 procedures planned per protocol.

### 8.10.2 Treatment Period

#### Part 1

Participants who meet selection criteria for enrollment will participate in Panel A, Panel B or Panel C after washing off their current atypical antipsychotic medication. Approximately 32 participants may be enrolled in Part 1.

On treatment days between Day 1 and Day 7, participants will be dosed once daily with MK-8189 or matching placebo and have procedures completed per the SoA. Participants will remain in the unit until Day 9 procedures are complete.

#### Part 2

**Participants with Schizophrenia:** Participants who meet selection criteria for enrollment will participate in Part 2 after washing off their current atypical antipsychotic medication. Up to approximately 16 participants will be enrolled in Panel D. In Panel E, 24 participants may be enrolled if more than 1 titration regimen is evaluated as described in Section 4.1. The intent is to have ~16 participants complete one titration regimen in Panel E.

**Healthy elderly participants:** Up to approximately 12 participants will be enrolled in Panel F. In Panel G, up to 20 participants may be enrolled if more than 1 titration regimen is evaluated as described in Section 4.1. The intent is to have ~12 participants complete one titration regimen in Panel G.

**Panel D/F Dose Regimen:** On treatment days between Day 1 and Day 13, participants will be dosed once daily with MK-8189 or matching placebo and have procedures completed per the SoA. Participants will remain in the unit until Day 15 procedures are complete.

**Panel E/G Titration Regimen 1:** On treatment days between Day 1 and Day 10, participants will be dosed once daily with MK-8189 or matching placebo and have procedures completed per the SoA. Participants will remain in the unit until Day 12 procedures are complete.

*Panel E/G Titration Regimen 2:* On treatment days between Day 1 and Day 7, participants will be dosed once daily with MK-8189 or matching placebo and have procedures completed per the SoA. Participants will remain in the unit until Day 9 procedures are complete.

*Panel E/G Titration Regimen 3:* On treatment days between Day 1 and Day 9, participants will be dosed once daily with MK-8189 or matching placebo and have procedures completed per the SoA. Participants will remain in the unit until Day 11 procedures are complete.

#### **8.10.3 Discontinued Participants Continuing to be Monitored in the Study**

At any point if a participant discontinues from treatment but continues to be monitored in the study, a subset of study procedures specified in the SoA may be completed at the discretion of the investigator and with Sponsor agreement. The subset of study procedures completed will be communicated in a PCL.

#### **8.10.4 Poststudy**

After completion of treatment, participants will resume the use of their own antipsychotic medication after the 48-hour postdose procedures are complete per the SoA and be discharged at the discretion of the investigator. A phone call should occur ~ 5 days after discharge from the unit to check for any side effects and medication compliance.

Participants will be required to return to clinic approximately 14 days after the last dose of study intervention for the poststudy visit. If the poststudy visit occurs less than 14 days after the last dose of study intervention, a subsequent follow-up telephone call should be made at 14 days post the last dose of study intervention to determine if any AEs have occurred since the poststudy clinic visit.

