In P005, for the primary endpoint of PANSS total score change from baseline at Week 4, although the MK-8189 group showed meaningful improvement in symptoms, the improvement missed statistical significance (difference [95% CI] in LS mean change was -4.7 [-9.8, 0.5];  $p=0.074$ ). Risperidone was superior to placebo with respect to this endpoint (difference [95% CI] in LS mean change was -7.3 [-14.0, -0.6];  $p=0.033$ ). There was no difference in magnitude of effect between MK-8189 and risperidone (difference [95% CI] in LS mean change was 2.6 [-4.0, 9.2];  $p=0.440$ ). For the exploratory endpoint of PANSS positive subscale score at Week 4, both MK-8189 and risperidone were superior to placebo. There was no significant difference in effect between MK-8189 and risperidone. Neither risperidone nor MK-8189 demonstrated significant improvement in the CGI-S.

Median Tmax of MK-8189 as monotherapy ranged from 10 to 20 hours with a t1/2 of approximately 8.4 hours (37.8% GCV).

Data suggest that the exposures at steady state for a given dose are generally lower in healthy participants compared to participants with schizophrenia administered MK-8189 as monotherapy.

In a DDI study (P006) the coadministration of extended release 240-mg diltiazem increased MK-8189 AUC and Cmax by approximately 2-fold and 1.3-fold, respectively, confirming that MK-8189 is a CYP3A substrate.

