### **8.4.1 Time Period and Frequency for Collecting AE, SAE, and Other Reportable Safety Event Information**

AEs, SAEs, and other reportable safety events that occur after the consent form is signed but before intervention allocation/randomization, must be reported by the investigator for randomized participants only if the event is the result of a protocol-specified intervention, including but not limited to washout or discontinuation of usual therapy, diet, placebo, or a procedure.

From the time of intervention allocation/randomization through 14 days following cessation of intervention, all AEs, SAEs and other reportable safety events must be reported by the investigator.

Additionally, any SAE brought to the attention of an investigator any time outside of the time period specified in the previous paragraph also must be reported immediately to the Sponsor if the event is considered related to study intervention.

Investigators are not obligated to actively seek AEs or SAEs or other reportable safety events in former study participants. However, if the investigator learns of any SAE, including a death, at any time after a participant has been discharged from the study, and he/she considers the event to be reasonably related to the study intervention or study participation, the investigator must promptly notify the Sponsor.

All initial and follow-up AEs, SAEs, and other reportable safety events will be recorded and reported to the Sponsor or designee within the time frames as indicated in [Table 3].

Table 3 Reporting Time Periods and Time Frames for Adverse Events and Other Reportable Safety Events

Type of Event	Reporting Time Period: Consent to Randomization/ Allocation	Reporting Time Period: Randomization/ Allocation through Protocol-specified Follow-up Period	Reporting Time Period: After the Protocol- specified Follow-up Period	Time Frame to Report Event and Follow-up Information to Sponsor:
NSAE	Report if: - due to protocol-specified intervention - causes exclusion - participant is receiving placebo run-in or other run-in treatment	Report all	Not required	Per data entry guidelines
SAE	Report if: - due to protocol-specified intervention - causes exclusion - participant is receiving placebo run-in or other run-in treatment	Report all	Report if: - drug/vaccine related. (Follow ongoing to outcome)	Within 24 hours of learning of event

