## **9.6 Statistical Methods**

### **Safety**

Summary statistics and plots will be generated for raw laboratory safety tests, 12-lead ECGs, and/or VS as well as for change from baseline, as deemed clinically appropriate. Depending on the safety parameter, the difference from baseline will either be computed on the original scale (raw change from baseline) or on the log scale and back-transformed for reporting (percent change from baseline). For vital signs, time-matched Day -1 readings will be used as baseline. For all other endpoints, baseline is defined as the predose Day 1 or Day -1 readings, as appropriate.

For both parts, summary statistics and plots will be generated for BARS, AIMS, SAS, VAS, and BPRS as well as for change from baseline. Responses to the C-SSRS will be listed.

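### In the schizophrenia panels, split the AE tables at antipsychotic restart and report the poststudy ratings as post-restart values

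*Combined protocol and SAP*

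**What the plan says.** - **Washout.** Section 8.1.5.1 takes participants off antipsychotics for at least 5 days or 3 half-lives, whichever is longer, before Day -1. This concerns the schizophrenia panels: Part 1, Panel D and Panel E.
- **Restart.** Section 8.10.4: "participants will resume the use of their own antipsychotic medication after the 48-hour postdose procedures are complete per the SoA".
- **AE window.** Section 8.4.1: "From the time of intervention allocation/randomization through 14 days following cessation of intervention, all AEs, SAEs and other reportable safety events must be reported".
- **Poststudy visit.** Section 8.10.4: "Participants will be required to return to clinic approximately 14 days after the last dose of study intervention for the poststudy visit". The schedules in Section 1.3 list BARS, AIMS, SAS, VAS and, for the schizophrenia panels, BPRS at a poststudy visit.
- **Analysis.** Section 9.4 takes adverse experiences of every type as primary safety endpoints. For the scales, Section 9.6 says "summary statistics and plots will be generated for BARS, AIMS, SAS, VAS, and BPRS as well as for change from baseline". Apart from vital signs, baseline is the predose Day 1 or Day -1 reading, which in these panels is an off-antipsychotic value.
- **What is not there.** Neither section gives an on-treatment AE cut-off, a split at restart, or a rule for the poststudy rating. Section 9.1 refers to Section 9.2 for full detail, but Section 9.2 only assigns responsibility for the analyses.

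**The concern.** Tolerability is the primary objective, and EPS are central to it. Dystonia and new or worsening tardive dyskinesia are events of clinical interest (Section 8.4.7), and the trial asks whether titration is needed to avoid dystonia (Section 2.1). Section 4.2.1.1 says that EPS are associated with antipsychotics and have also been seen with MK-8189. Restarting an antipsychotic can therefore produce the same kinds of event that the trial is there to count.

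Without a split, an akathisia that begins a week after restart is counted in the MK-8189 column just like one that begins on Day 3. The poststudy change from baseline has a related problem: it subtracts an off-antipsychotic value from an on-antipsychotic one, so it cannot be read as an effect of MK-8189. At stake are the absolute AE rates reported for MK-8189 and the reading of individual EPS events.

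**Working it through.** The plan states no figure for the share of follow-up after restart, so there is none to reproduce.

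**1. Share of AE-collection time after restart.** Let L be the day of the last dose (Section 8.10.2). Restart is at about L + 2 and collection ends at L + 14, which leaves 12 days after restart. Elapsed time from Day 1 to the end is L + 13 days, so the share is 12/(L + 13).

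| Panel | L | Share, elapsed days | Share, calendar days, 12/(L + 14) |
|---|---|---|---|
| Part 1 and Panel E Regimen 2 | 7 | 12/20 = 60% | 12/21 = 57% |
| Panel E Regimen 3 | 9 | 12/22 = 55% | 12/23 = 52% |
| Panel E Regimen 1 | 10 | 12/23 = 52% | 12/24 = 50% |
| Panel D | 13 | 12/26 = 46% | 12/27 = 44% |

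Panels F and G have no antipsychotic to resume, so their share is 0%.

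**2. Ratings.** The 48-hour ratings precede restart. Only the poststudy rating follows it: about 1 in 4 to 1 in 6 of the scheduled post-baseline ratings (17-25%). This count comes from schedule tables that were damaged in extraction and is approximate.

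**3. Drug remaining at restart.** Section 2.2.2 gives a half-life of about 8.4 h (geometric CV 37.8%) and a median Tmax of 10 to 20 h.
- Decline counted from dosing: 48/8.4 = 5.7 half-lives, and 0.5^5.7 is about 2%.
- Decline counted from Tmax, over 38 or 28 h: about 4% or 10%.
- With a half-life of 15.3 h, an assumed 95th percentile = 8.4 × exp(1.645 × √ln(1 + 0.378²)): 11% from dosing, 18% or 28% from Tmax.

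Exposure at restart is low, but not always negligible.

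**4. Effect on the randomized difference.** Let a and b be the on-drug event probabilities on MK-8189 and placebo, and r the probability of an event from restart, the same in both arms and independent of earlier events. Reported over the whole window:
- active: 1 − (1 − a)(1 − r) = a + r(1 − a)
- placebo: b + r(1 − b)
- difference: (a − b)(1 − r)

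For assumed r of 5%, 10% and 20%, the difference keeps 95%, 90% and 80% of its size. Both absolute rates rise.

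**5. Can the placebo group show the background?** Table 2 in Section 6.3.1 gives 12 active and 4 placebo participants per schizophrenia panel or regimen. Suppose MK-8189 causes no EPS and restart causes them with probability r in both arms. The chance of at least one event on active and none on placebo is [1 − (1 − r)^12] × (1 − r)^4:
- r = 5%: 0.460 × 0.815 = 37%
- r = 10%: 0.718 × 0.656 = 47%
- r = 20%: 0.931 × 0.410 = 38%

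The documents give no value for r, so these rates are assumptions. Across the range, a panel would show events on MK-8189 only, with no drug effect, in more than a third of cases.

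**The case against.** The case on the other side has several sound parts.

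- **Randomized placebo under the same restart rule.** This stands. Step 4 shows that the contrast loses little. It does not settle single events, because 4 placebo participants give too poor an estimate of the background (step 5).
- **The decisive tolerability data come before restart.** This stands. Section 2.1 places dystonia near peak concentration, and the reviews in Sections 4.1 and 6.6 fall within the dosing days. The gap affects final reporting, not titration decisions.
- **Restart may cause few events.** Participants resume a drug of their own, must have tolerated antipsychotics before (criterion 10), and had no clinically significant change of drug or dose for 2 months before screening (criterion 9a). This is fair, and it is why no particular restart rate is claimed.
- **Attribution is partly handled.** Concomitant medication is recorded (Section 8.1.5.2) and the causality assessment weighs other drugs (Section 10.3.4). That is a judgement on each event; it does not separate tables of all AEs.
- **The scales may be summarized by visit.** The plan does not say that visits are pooled. If summaries are by visit, the poststudy value already stands apart and needs only a label.

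A reader might go further and infer that 46-60% of the safety data measure the antipsychotic rather than MK-8189. The documents do not support that: the figure is a share of days, dosing-period events and all but one scheduled rating precede restart, and late or discontinuation effects of MK-8189 can still appear afterwards. Nor do they support the inference that a patient-versus-healthy safety comparison is spoiled. No such comparison is planned; the population comparisons in Section 9.6 concern PK only.

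**Conclusion.** The point holds as a reporting gap in the schizophrenia panels. Between 46% and 60% of elapsed AE-collection days follow antipsychotic restart, and the plan does not separate them. Events caused by restart would raise the absolute AE rates shown for MK-8189, and individual EPS events after restart cannot be attributed cleanly. The poststudy change from baseline mixes on- and off-antipsychotic states. The randomized difference is little affected, and Panels F and G are not affected at all.

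The shares assume a completed course, a window starting at Day 1 and restart at 48 hours; a later restart lowers them. It would be too strong to call the period after 48 hours drug-free: the 2% figure ignores Tmax and half-life variability, and carrying the 8.4 h half-life over to elderly participants is itself an assumption. This is a worthwhile, inexpensive improvement rather than a flaw that invalidates the trial.

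**What to change.** In Sections 9.4 and 9.6, for Part 1 and Panels D and E:

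1. Keep the overall AE table. Beside it, tabulate AEs by arm and by onset in two periods: first dose to actual antipsychotic restart, and restart to 14 days after the last dose.
2. Report poststudy BARS, AIMS, SAS, VAS and BPRS as post-restart values, outside the on-treatment change-from-baseline summaries and plots.
3. Confirm that the restart date is captured with concomitant medication. Section 8.1.5.2 says that medication is recorded but does not mention dates.
4. Reconcile inclusion criterion 12 (Section 5.1), which has participants off antipsychotics throughout the study period, with the restart in Section 8.10.4.

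Leave AE collection as it is. Panels F and G need no 48-hour cut; at most, a supportive table could use one.

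The cost is SAP wording, one date variable and some extra tables. The downside is that some late or discontinuation effects of MK-8189 will appear in the second period; keeping the overall table means they are not lost.
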